10.0 MEASUREMENT OF EFFECT**10.1 Ipsilateral Reconstruction Complications**

Reconstruction complications will be defined as:

- Capsular contracture (Baker Grade III or IV only)
- Complete failure of the implant/skin flap
- Unplanned admission for reconstruction related issue(s) including but not limited to infection, wound healing complication or pain
- Unplanned return to the operating room for recon related issue including but not limited to infection, prosthesis exposure, failed reconstruction, implant removal, wound healing complications or contracture management

Note: Complications related to the contralateral breast will be collected but will not count towards the assessment of the primary endpoint, ipsilateral breast complications will be counted towards the primary endpoint.

10.2 Acute and Late Radiation Complications

Acute Adverse Events: Acute adverse events, will be scored per CTCAE 4.0 regardless of attribution. Attribution will however be collected for separate analysis.

Late Radiation Adverse Events: Late radiation complications will be defined as those that are present ≥ 6 months after the final dose of radiation and include CTCAE 4.0 grade 3+:

10.3 Criteria for Disease Response

Local and regional recurrences: A recurrence will be classified as local if it recurs on the chest wall (local) or reconstructed breast. Local regional recurrence will be classified for the axillary, supraclavicular, infraclavicular or ipsilateral internal mammary lymph nodes, and distant recurrence for elsewhere.

10.3.1 Local Recurrence

Local recurrence is defined as histologic evidence of ductal carcinoma in situ or invasive breast cancer in the ipsilateral reconstructed breast or chest wall.

10.3.2 Regional Recurrence

Regional recurrence is defined as the cytologic or histologic evidence of disease in the ipsilateral internal mammary, ipsilateral supraclavicular, ipsilateral infraclavicular and/or ipsilateral axillary nodes or soft tissue of the ipsilateral axilla.

10.3.3 Distant Recurrence

Distant recurrence is defined as the cytologic, histologic and/or radiographic evidence of disease in the skin, subcutaneous tissue, lymph nodes (other than local or regional metastasis), lung, bone marrow, central nervous system or histologic and/or radiographic evidence of skeletal or liver metastasis.

10.3.4 Second Primary Breast Cancer

Second primary breast cancer is defined histologic evidence of ductal carcinoma in situ or invasive breast cancer in the contralateral breast or chest wall.

10.3.5 Second Primary Cancer (Non-breast)

Any non-breast second primary cancer other than squamous or basal cell carcinoma of the skin, melanoma in situ, or carcinoma in situ of the cervix is to be reported and should be confirmed histologically whenever possible.

10.3.6 Death

Underlying cause of death is to be reported.

10.4 Patient Reported Outcomes

Patient-reported assessments of cosmesis, lymphedema, well-being, and satisfaction with treatment will be collected at the time points listed below. Each questionnaire that will be administered in this study is described in the following sections.

These self-reported questionnaires will require approximately 30 to 45 minutes for completion at all time points. We estimate The BREAST-Q questionnaire requires 10-15 minutes for completion, the Was It Worth It questionnaire requires 1-3 minutes, the lymphedema questionnaires require 5-10 minutes, the photography requires 5-10 minutes, and the health care utilization 5-10 minutes.

10.4.1 Breast Q survey ([Appendix II](#))

We will be using the Breast Q survey tool (section V 2.0) to assess patient-reported cosmesis, well-being, and satisfaction. [81-83] This tool has been validated for use in patients before and after mastectomy with reconstruction, and is provided free of charge for academic research. We will be using the Breast Q Post Mastectomy or Post Reconstruction (if already reconstructed) Module at

prior to radiation therapy and the Breast Q Post Reconstruction Module at 2 and 5 years (+/- 2 months) after radiation finishes. There are 62 items in the post-mastectomy module and 116 items in the post-reconstruction module (but an individual patient will only complete those that apply to her specific type of reconstruction). These modules are currently available in 16 languages, but for this study we will be limiting enrollment to patients who can consent to participation in English language only (for US), in addition to patients who can read and comprehend French, from CCTG institutions. The conceptual framework of the BREAST-Q modules is comprised of two overarching themes, which are health-related quality of life (QOL) and patient satisfaction.

Within QOL, there are three scales: Physical, Psychosocial and Sexual Well-being. Within the Psychosocial Well-being scale for patients with breast reconstruction planned or already performed, there are items that ask about body and a woman's confidence in social settings. Other items cover emotional health and self-esteem. Within the Sexual Well-being scale, there are items that ask about feelings of sexual attractiveness when clothed and unclothed and sexual confidence as it relates to one's breasts, as well as how comfortable or at ease a woman feels during sexual activity. Within the Physical Well-being scales (one for Upper Body and one for Abdomen and Trunk), there are questions asking about pain, activity limitations, and sleep problems due to discomfort, as well as abdominal discomfort, bloating, bulging, and difficulty doing certain activities due to abdominal weakness.

Within patient satisfaction, there are three other scales: Satisfaction with breasts/nipples/abdomen, Satisfaction with overall outcome and Satisfaction with Care. There are three breast/nipple/abdomen satisfaction scales that are administered depending on the type of reconstruction: in the Satisfaction with breasts scale, there are questions regarding how comfortably bras fit, and how satisfied a woman is with her breast area both clothed and unclothed. There are also implant-specific items (e.g., amount of rippling that can be seen or felt). In the Satisfaction with nipples scale (to be completed only by those who underwent nipple reconstruction), there are items covering shape, color, projection and how natural the reconstructed nipple looks. In the Satisfaction with abdomen scale (to be completed only following autologous tissue breast reconstruction with TRAM or DIEP flap), there are items asking about overall appearance as well as position of navel (belly button) and scars. In the Satisfaction with outcome scale, there are items asking about whether or not expectations were met with respect to the aesthetic outcome and the impact reconstruction has had upon her life as well as satisfaction with the decision to have reconstruction (e.g. "I would do it again"). The Satisfaction with Care scale will not be included in this study.

Each scale can be used independently and scored separately. The BREAST-Q scoring software, QScore, transforms patient-reported data into summary scores ranging from 0-100 with a higher number meaning better quality of life or higher satisfaction on the various scales.

BREAST Q questionnaires are currently completed with pencil and paper. Patients will be asked to complete these at a clinic visit, but patients who are unable to receive and/or complete this survey in clinic will be allowed to receive and/or return this survey by mail.

10.4.2 Was It Worth It Questionnaire ([Appendix V](#))

The Was It Worth It questionnaire will assess satisfaction with participation in a research trial. It will be administered at 24 months (+/- 2 months) after the final dose of radiation.

10.5 Lymphedema

Lymphedema assessments (i.e., bilateral arm circumference measurements) will be administered before radiation, 6 months after radiation and then again at 2 years after completion of radiation therapy. Body mass index (BMI) will also be ascertained. Lymphedema questionnaires will be completed as described in Section 10.5.2. Patients who develop a new or recurrent breast cancer will discontinue the arm lymphedema assessments.

10.5.1 Clinical Assessment

All planned lymphedema evaluations will include clinical assessment for signs and symptoms of lymphedema. Any patient complaining of “arm swelling” or “heaviness” or showing signs of extremity swelling (≥ 2 cm difference between upper extremities at any measurement point) will be treated according to current practice guidelines and referred to a lymphedema health care provider. In addition, patients will be instructed to call their oncologist if they develop any new arm symptoms during the periods between planned assessments. Such patients will be scheduled for immediate evaluation and arm measurements.

Arm Measurement: Circumferential measurement of limb volume will be performed on both affected and non-affected arms. Patients will sit with the arms resting horizontally palms-down on a bedside table placed at a level slightly below the axilla. The patients will be instructed to wear loose sleeves or short sleeves/sleeveless tops and to remove any arm jewelry prior to the measurement. Measurements will be taken at the wrist, half way between the wrist and antecubital fossa (below the elbow), at the antecubital fossa, half way between the antecubital fossa and the axilla, and at the axilla. In all cases, the plane of the tape around the arm will be held perpendicular to the long axis of the arm and perpendicular to the floor. The tape will be held snugly around the body part without indenting the skin or compressing subcutaneous adipose tissue. If gaps between the skin and tape are seen in some individuals, tension should not be increased to reduce the gap. Arm measurements and other required data will be recorded on the Arm circumference measurement case report form (Appendix IV) which is to be completed by the local study coordinator. The standard formula (based on cylindrical slices) will be utilized in this study to calculate volume (V) from circumference (U) measures.

PowerPoint slides located on the A221505 study page will provide instructions on how to perform these measurements. The procedures used in CALGB 70305 will be followed in this study.

Arm Lymphedema: A patient will be considered to have mild lymphedema if she has symptomatic arm swelling or heaviness with less than a 10% increase in volume of the ipsilateral arm from pre-radiation volume.

We will consider two different measures of arm lymphedema as secondary endpoints in this study. As a second measure of arm lymphedema, we will consider the percent change in ipsilateral arm volume post-radiation from its pre-radiation volume. The impact of lymphedema based on extent of surgery (sentinel vs. axillary dissection) has been reported elsewhere and therefore will not be focus of this study.

Breast Lymphedema: While upper extremity lymphedema is a recognized complication following axillary surgery for breast cancer, breast lymphedema can also occur and be associated with significant morbidity. To date, this condition has not been highlighted primarily because the objective measurement and diagnostic criteria have largely been unavailable. The most common criteria used are based on clinical signs of diffuse skin edema and erythema. Reconstructed breast edema will be captured in the CTCAE late morbidity reporting as well as in the cosmesis evaluation and the LBCQ questionnaire (Section 10.5.2).

10.5.2 Patient Completed Lymphedema Questionnaires ([Appendix III](#))

The Lymphedema and Breast Cancer Questionnaire (LBCQ) short form and Breast Lymphedema (BLE) Symptom Survey will be offered to all patients, and administered before radiation, 6 months after radiation and then again at 2 and 5 years after completion of radiation therapy.

The Lymphedema and Breast Cancer Questionnaire (LBCQ) short form consists of 19 symptom-related questions. Armer et al. initially developed, piloted, and revised the LBCQ-Part I as a semi-structured interview tool to assess signs and symptoms of lymphedema [52]. Subsequently, expert patient educators, clinicians, and researchers reviewed and revised the LBCQ for clarity, simplicity of format, and complete coverage of the symptom domain. The final LBCQ Part I ended up consisting of 19 symptom-related questions to which patients respond to the interviewer with "yes/no" answers regarding whether the symptom is currently present (today or within the past month) or has been present at any point in the past year. Scores are calculated for the frequency of the total number of current symptoms and the total number of symptoms in the past year. Validity of this instrument was confirmed through studies that found it was able to differentiate healthy women and women with known breast cancer lymphedema. The instrument was also found to be predictive of the development of limb swelling in a sample of breast cancer survivors with yet-undetermined lymphedema status. [67] The LBCQ questionnaire should be administered by trained institutional research staff. However, if the patient self-completes the questionnaire, a member of the study research team who is knowledgeable about the study, should be available to instruct, answer questions, and review the questionnaire for completeness.

The **Breast Lymphedema (BLE) Symptom Survey** has also been included to rate severity of symptoms of the chest wall or reconstructed breast for heaviness, discomfort, redness, swelling and associated degree of distress using a 10-point scale ('Not at all'=0 to 'A lot'=10). This has been extrapolated in the reconstructed breast setting from women undergoing breast conservation. In a prospective study of 124 women who underwent breast-conserving operations, women who were clinically diagnosed with BLE reported more symptoms than women without BLE (mean 2.6 versus 1.3, $p < 0.0001$). Two or more symptoms included on the questionnaire were reported by 81% of women with BLE compared to 35% of women without BLE. Women with BLE also had significantly higher severity scores for breast heaviness, redness, and swelling. By physical exam, 100% of women with BLE had skin edema compared to 11.6% of those without BLE, ($p < 0.0001$). Similarly, breast erythema was seen in 79% of those with BLE compared to 13% without BLE, $p < 0.0001$ [68].

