12.4.4 Patient Reported Outcomes (PRO) Objectives

Physical well-being, psychosocial well-being, sexual well-being, satisfaction with breast/nipples/abdomen, and satisfaction with overall outcome between the treatment arms at 24 months after radiation: Change in LBCQ and BLE scores at 24 months post-radiation (relative to pre-RT) and patient satisfaction scores as measured by the Breast Q overall outcome scale will be summarized and will be compared across the treatment arms using a two-sample t-test with a two-sided alternative. Linear mixed models will also be used to assess these scores longitudinally.

Patient satisfaction with trial participation by treatment arm as measured by the Was It Worth It Questionnaire at 24 months after radiation: Was It Worth It questionnaire responses to each of the five questions at 24 months will be summarized and will be compared across treatment arms using a Chi-square tests with a two-sided alternative. In particular, for questions 1-3, the proportion of patients who answered “yes” will be compared across the two treatment arms, and for questions 4 and 5, we will compare the proportion of patients who answered “it got worse” and “worse than I expected” (respectively) across the two arms.

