APPENDIX III: PATIENT COMPLETED LYMPHEDEMA MEASURES

Lymphedema and Breast Cancer Questionnaire (LBCQ)-Baseline and 6-month visit

Answer all questions you understand. Do not answer questions that have any words you do not understand. Circle any words you do not know. **Lymphedema** means swelling of the arm, hand, shoulder or upper body on the side where your cancer was found. Today means today or in the past 30 days.

Do you have limited movement of your . . .	Today If yes, please describe	During Past 6 months If yes, please describe
1. Shoulder?	No  Yes 	No  Yes 
2. Elbow?	No  Yes 	No  Yes 
3. Wrist?	No  Yes 	No  Yes 
4. Fingers?	No  Yes 	No  Yes 
5. Does your arm or hand feel weak?	No  Yes 	No  Yes 

The following questions pertain to arm, breast, and chest symptoms.

Have you experienced:	Today	During Past 6 months	What action you did for this symptom: Please describe
6. Tenderness?	No  Yes 	No  Yes 	No action  Action:
7. Swelling?	No  Yes 	No  Yes 	No action  Action:

8. Swelling with pitting? (Pitting is when you press firmly on your skin and the dent stays long enough to feel it when you slide the pad of your finger across it.)	No  Yes 	No  Yes 	No action  Action:
9. Redness?	No  Yes 	No  Yes 	No action  Action:
10. Blistering?	No  Yes 	No  Yes 	No action  Action:

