11. Firmness/tightness?	No  Yes 	No  Yes 	No action  Action:
12. Increased temperature in your arm?	No  Yes 	No  Yes 	No action  Action:
13. Heaviness?	No  Yes 	No  Yes 	No action  Action:
14. Numbness?	No  Yes 	No  Yes 	No action  Action:
15. Stiffness?	No  Yes 	No  Yes 	No action  Action:
16. Aching?	No  Yes 	No  Yes 	No action  Action:
17. Chest wall swelling?	No  Yes 	No  Yes 	No action  Action:

18. Chest wall or reconstructed breast swelling? (N/A if no breast)	No  Yes  n/a 	No  Yes  n/a 	No action  Action:
19. Pocket of fluid develop?	No  Yes 	No  Yes 	No action  Action (for example, how many times drained):
20. Other Symptoms?	No  Yes 	No  Yes 	No action  Action:

Lymphedema and Breast Cancer Questionnaire (LBCQ)-2 year and 5 year visit

Answer all questions you understand. Do not answer questions that have any words you do not understand. Circle any words you do not know. Lymphedema means swelling of the arm, hand, shoulder or upper body on the side where your cancer was found. Now means today or in the past 30 days.

Do you have limited movement of your . . .	Now If yes, please describe	During the Past Year If yes, please describe

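### The LBCQ recall score uses a 6-month window up to 6 months after radiation and a 12-month window at 2 and 5 years, so its planned change score and time effect mix two scales

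*Combined protocol and SAP*

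**What the plan says.** Section 10.5.2 describes the LBCQ as 19 yes/no symptom questions, each asking whether "the symptom is currently present (today or within the past month) or has been present at any point in the past year". It derives two totals: "Scores are calculated for the frequency of the total number of current symptoms and the total number of symptoms in the past year". The questionnaire is "administered before radiation, 6 months after radiation and then again at 2 and 5 years after completion of radiation therapy".

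Appendix III prints two versions of the form:

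- Baseline and 6-month version: a Today column, and a recall column headed "During Past 6 months If yes, please describe".
- 2-year and 5-year version: a Now column, and a recall column headed "During the Past Year If yes, please describe".

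Each version defines its first column as today or the past 30 days.

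Section 12.4.4 plans to summarise "Change in LBCQ and BLE scores at 24 months post-radiation (relative to pre-RT") and to compare it between arms with a two-sided two-sample t-test. It adds: "Linear mixed models will also be used to assess these scores longitudinally". It does not say which of the two LBCQ totals is meant, does not mention that the recall window changes, and lists no model terms.

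**The concern.** A count of symptoms experienced at any time in a window can only stay the same or grow as the window lengthens. If the 24-month recall count covers 12 months and the pre-RT count covers 6, their difference contains a component that comes from the form rather than from the patient. The same step falls between the 6-month and 2-year visits in the longitudinal model. Pre-RT against 6 months, and 2 years against 5 years, are each like for like.

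Two things are at stake for the recall score. The within-arm change and the time effect cannot be read as symptoms getting better or worse after radiation. And a real difference between arms would be expressed in different units at 6 months than at 2 and 5 years. Because the score is not named, the choice between an affected and an unaffected total is left open in an unblinded trial.

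**Working it through.** **Side-by-side reading**

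| Visit | Current column | Recall column | Past-year score of 10.5.2 |
|---|---|---|---|
| Pre-RT | 30 days | 6 months | not obtainable |
| 6 months | 30 days | 6 months | not obtainable |
| 2 years | 30 days | 12 months | obtainable |
| 5 years | 30 days | 12 months | obtainable |

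So the current-symptom total is comparable at all four visits, and the recall total is not.

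**Size**

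The documents give no LBCQ symptom rates, standard deviation, effect size or power, so there is no planned figure to reproduce. What follows is illustration. The only input from the documents is the 19 questions (10.5.2); every rate is an assumption.

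*Model A: constant frequency, two 6-month periods.* A proportion p of patients report an item in any 6 months.

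- 6-month count = 19p. With independent periods, 12-month count = 19[1 − (1 − p)²].
- p = 0.05: 0.95 and 1.85, artefact 0.9.
- p = 0.15: 2.85 and 5.27, artefact 2.4.
- p = 0.30: 5.70 and 9.69, artefact 4.0.
- If half of symptoms persist, the artefact is 19 × 0.5 × p(1 − p), or about 0.5, 1.2 and 2.0.
- If all persist, it is 0.

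*Model B: constant prevalence p, new-onset rate λ per symptom-free month.* Expected count over T months = 19[1 − (1 − p)exp(−λT)].

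- p = 0.15, λ = 0: 2.85 on both forms, artefact 0.
- p = 0.15, λ = 0.02: 19(1 − 0.85e^−0.12) = 4.68 and 19(1 − 0.85e^−0.24) = 6.30, artefact 1.62.
- Over p from 0.05 to 0.30 and λ from 0 to 0.05, the artefact runs from 0 to about 3.5 items.

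**Direction of the observed change.** Take p = 0.15 and let λ be 0.05 before radiation and 0.02 at 24 months. The pre-RT 6-month count is 7.04 and the 24-month 12-month count is 6.30, an observed change of −0.74. On a 6-month window at both visits it would be 4.68 − 7.04 = −2.36. The bias is upward (+1.62), yet the score still falls.

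**Between-arm test under the null.** A simulation used 396 patients per arm (the evaluable target in 12.2), 4,000 runs, p = 0.15, λ = 0.02 with patient-level variation in the rate, and the forms as printed. Mean within-arm change was about +1.50 items, mean between-arm difference 0.00, and type I error 0.0485 at a two-sided 5% level.

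**Between-arm scale when the arms differ.** Take p = 0.15 and λ = 0.02 against 0.01.

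- 6-month window: 3.79 − 4.68 = −0.89 items.
- 12-month window: 4.68 − 6.30 = −1.62 items.

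The same underlying difference in onset rate gives a contrast nearly twice as large on the 12-month form. A single arm effect averaged over visits would mix the two.

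**The case against.** The strongest reply is that the planned inference is between arms. Both arms receive the same forms at the same visits, so the shift is common to both and cancels. Under randomisation the baseline term also cancels in expectation, which leaves the arm difference in the 24-month past-year count, an interpretable quantity. A categorical visit term would absorb the common shift in the mixed model. All of this stands for the null between-arm test. It does not rescue the summarised change, the visit effect, or an arm effect pooled over visits, and 12.4.4 does not specify the terms that would keep visits apart.

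Second, 12.4.4 never selects the recall score, and the past-year sentence in 10.5.2 may describe the instrument rather than this trial's scoring. That limits the point to one of two scores. But 10.5.2 contains the only LBCQ scoring rule, it names the past-year total, and that total cannot be formed from the pre-RT and 6-month forms.

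Third, a 6-month window at the 6-month visit is sensible, because a full year would reach back before radiation. That is a good reason to leave the forms alone. It is not a reason to subtract across windows.

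Some stronger readings are tempting and are not supported:

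- A reader might infer that the recall score must rise with time by construction. Patients register after mastectomy and may be symptomatic before radiation; a real fall can outweigh the wider window, as shown above.
- A reader might infer that the arm comparison is biased. With identical arms, it is not.
- A reader might infer from the wording "18. Chest wall or reconstructed breast swelling? (N/A if no breast") that items 17 and 18 count the same swelling twice and should be merged. The documents do not say how a not-applicable answer is scored, the general swelling question (item 7) overlaps as well, and merging would alter a 19-question instrument whose validity 10.5.2 relies on. No such change is proposed.

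**Conclusion.** The point holds for the LBCQ recall score only. Section 10.5.2 and the Appendix III forms contradict each other, and applying 12.4.4 to the recall score would compare a 12-month count with a 6-month count. Within-arm change is biased upward by roughly 0 to 4 of 19 items. That range rests wholly on assumed rates and a stable symptom process; it is zero if symptoms are fully persistent and largest if 6-month periods are independent. Any real arm difference changes scale between the 6-month visit and the 2- and 5-year visits. The current-symptom score is sound as collected. LBCQ change is a secondary patient-reported outcome, so the primary endpoint and the sample size are untouched.

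**What to change.** In 12.4.4:

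- Name the current-symptom count (the Today/Now column, past 30 days) as the LBCQ score for change from pre-RT and for the mixed model.
- Compare the recall count between arms only within a visit, with the baseline count as covariate, and do not report it as a change or a trend. As a covariate, the baseline count does not need the same window as the outcome.

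In 10.5.2, state the recall window that each form actually uses, so that the scoring text and Appendix III agree.

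The cost is wording only. The current-symptom column is already on both forms, so no new data are needed. The small downside is that short-lived symptoms arising and resolving between visits drop out of the longitudinal score; they remain visible in the within-visit recall comparison when they fall inside that form's window.
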